3.1.1.4 Open-label Period

Subjects will be given the option to enter the OLP if they:

- 1 Complete 197 days of the RCP, or
- 2 Experience an AC-determined NMO/NMOSD attack during the RCP, or
- 3 Are in the RCP at the time when 67 AC-determined attacks have occurred
- 4 Are in the RCP when enrollment is discontinued upon recommendation of the DMC based on evidence of efficacy and safety (see Section 4.4).

Subjects who discontinue from the RCP for reasons other than one of the reasons above will not be eligible for the OLP. Reasons for subjects not entering the OLP will be captured. These subjects will be followed for safety in the SFP.

The first day of the OLP will be Day 1 (OLP Day 1). Upon entering the OLP for one of the three reasons outlined above, subjects will receive MEDI-551 as described in Table 2. During the OLP, subjects will be followed at scheduled study visits and will initiate or continue on MEDI-551 therapy per Table 7. The OLP will continue for a maximum of 3 years (after the last subject enters), until regulatory approval for MEDI-551 in each participating country or until the Sponsor discontinues development of MEDI-551 in this indication, whichever occurs first. Subjects can choose to exit the OLP at any time for any reason, including seeking alternative treatment options, at which point they will enter the SFP (unless consent is withdrawn).

Subjects will be followed for NMO/NMOSD attacks in the same fashion as in the RCP and events will be centrally adjudicated.

3.1.1.5 Safety Follow-up Period

The SFP will start when a subject prematurely discontinues from the RCP or OLP. The length of the SFP will be determined by the time elapsed from the time of the last dose of the investigational product to the time of the premature discontinuation, to complete a total of 52 weeks. During the SFP, the subject will be monitored for AEs/serious adverse events (SAEs), B-cell levels, ADAs, and immunoglobulin levels.

During the SFP, a subject may receive standard treatment for their NMO/NMOSD at the discretion of the investigator.

3.1.2 Treatment Regimen

Randomized-controlled Period

Subjects will be randomized in a 3:1 ratio to receive MEDI-551 or placebo during the 197 days of the RCP as described in Table 1.

Table 1 Randomized-controlled Period Treatment Regimen

Treatment Arm	Treatment Regimen
1	300 mg IV MEDI-551 on Day 1 and Day 15
2	IV Placebo on Day 1 and Day 15

IV = intravenous

Investigational product will be administered as a 90-minute IV infusion via an infusion pump. All subjects in the placebo and MEDI-551 arms will be premedicated on Day 1 and Day 15 with IV methylprednisolone (80-125 mg or equivalent glucocorticoid), oral (PO) diphenhydramine (25-50 mg or equivalent antihistamine), and PO paracetamol (acetaminophen; 500-650 mg) prophylactically to prevent infusion reactions. Sites should utilize local supplies of the premedications where possible. The Sponsor will provide reimbursement during the study.

Additionally, all subjects entering the RCP will be treated for 2 weeks (Day 1 to Day 14) with oral corticosteroids (prednisone 20 mg/day or equivalent oral glucocorticoid). A tapering schedule will be implemented from Day 15 to Day 21 (see Section 4.5.2).

Open-label Period

All subjects who enter the OLP will receive open-label MEDI-551. In order to provide subjects who were receiving placebo during the RCP with 2 doses of MEDI-551 (OLP Day 1 and OLP Day 15) and to ensure maintaining the masking of the study, subjects who were in Treatment Arm 1 (MEDI-551) or Treatment Arm 2 (placebo) will be dosed as described in Table 2.

Table 2 Open-label Period Treatment Regimen

Treatment Arm in RCP	Treatment Regimen
1	300 mg IV MEDI-551 on OLP Day 1, masked IV placebo OLP Day 15, then 300 mg IV MEDI-551 Q26W thereafter ^a
2	300 mg IV MEDI-551 on OLP Day 1, masked 300 mg IV MEDI-551 on OLP Day 15, then 300 mg IV MEDI-551 Q26W thereafter ^a

IV = intravenous; OLP = Open-label Period; Q26W = every 26 weeks; RCP = Randomized-controlled Period; SFP = Safety Follow-up Period.

^a The OLP will continue for a minimum of 1 year after the last subject enters and a maximum of 3 years (after the last subject enters), or until regulatory approval for MEDI-551 in the participating country, or until the Sponsor discontinues development of MEDI-551 in this indication, whichever occurs first. Subjects can choose to exit the OLP at any time for any reason, including seeking alternative treatment options, at which point they will enter the SFP (unless consent is withdrawn).

Dosing of subjects enrolling into the OLP following an adjudicated NMO/NMOSD attack, following the occurrence of the 67th adjudicated NMO/NMOSD attack, or following

discontinuation of enrollment upon recommendation of the independent DMC based on evidence of efficacy and safety, will follow the OLP dosing regimen as detailed above in Table 2.

Investigational product will be administered as a 90-minute IV infusion via an infusion pump. All subjects will be premedicated on OLP Day 1 and OLP Day 15 and at subsequent dosing visits with IV methylprednisolone (80-125 mg or equivalent glucocorticoid), PO diphenhydramine (25-50 mg or equivalent antihistamine), and PO paracetamol (acetaminophen; 500-650 mg) prophylactically to prevent infusion reactions. Sites should utilize local supplies of the premedications where possible. The Sponsor will provide reimbursement during the study.

3.1.3 Management of Study Medication Related Toxicities

Infusion-related reaction is the only identified risk of IV MEDI-551 to date and has occurred in both MEDI-551 oncology and non-oncology studies. For subjects experiencing an infusion-related reaction, an approach to these reactions based on severity of symptoms is presented in Table 3 and Appendix 2 (National Institute of Allergy and Infectious Diseases [NIAID] and Food Allergy and Anaphylaxis Network [FAAN] Guidance for Anaphylaxis Diagnosis), with suggested treatment options. Final treatment is at the discretion of the investigator and should reflect local standard of care.

Table 3 An Approach to Management of Anaphylactic, Hypersensitivity, and Infusion Reactions

Severity of Symptoms	Treatment	Investigational Product

Mild reactions (infusion and hypersensitivity) Mild infusion reactions such as headache, nausea, nonpruritic rash, or mild hypersensitivity reactions including localized cutaneous reactions such as mild pruritus, flushing, rash, dizziness, headache, ≤ 20 mmHg change in systolic BP from pre-infusion measurement
	
 • Evaluate subject, including close monitoring of vital signs • At the discretion of the investigator, treat subject, for example, with: 
 • Normal saline (~500-1000 mL/hour IV) and/or • Diphenhydramine 50 mg IV or equivalent and/or • Acetaminophen 500-650 mg or equivalent dose of paracetamol and/or • Topical antihistamines and/or low-potency topical corticosteroid preparations and/or • Anti-nausea medication, as needed 	
 • Stop IP infusion immediately • Once the event has resolved, resume current IP infusion under observation and complete IP infusion at no more than half the planned infusion rate

Moderate reactions (infusion) Infusion reaction such as those listed above under mild reactions but excluding moderate hypersensitivity reactions (see below)
	
 • Evaluate subject, including close monitoring of vital signs • Treat subject, for example, with: 
 • Normal saline (~500-1000 mL/hour IV) and/or • Diphenhydramine 50 mg IV or equivalent and/or • Acetaminophen 500-650 mg or equivalent dose of paracetamol and/or • Anti-nausea and/or antiemetic intramuscular, as needed 	
 • Stop the infusion immediately • Once the event has resolved, resume current IP infusion under observation and at no more than half the planned infusion rate after treatment of current signs and symptoms as suggested

Moderate hypersensitivity reactions Infusion reactions which may include generalized rash or urticaria, palpitations, chest discomfort, shortness of breath, hypo- or hypertension with > 20 mmHg change in systolic BP from pre-infusion measurement
	
 • Evaluate subject, including close monitoring of vital signs • Treat subject, for example, with: 
 • Normal saline (~500-1000 mL/hour IV) and/or • Diphenhydramine 50 mg IV or equivalent and/or • Acetaminophen 500-650 mg or equivalent dose of paracetamol and/or • IV corticosteroids, such as hydrocortisone 100 mg or methylprednisolone 20-40 mg 	
 • Stop the infusion immediately • Once the event has resolved, resume current IP infusion under observation and at no more than half the planned infusion rate after treatment of current signs and symptoms as suggested

Table 3 An Approach to Management of Anaphylactic, Hypersensitivity, and Infusion Reactions

Severity of Symptoms	Treatment	Investigational Product

Severe
 
Above plus fever with rigors, hypo- or hypertension with ≥ 40 mmHg change in systolic BP, signs of end organ dysfunction (eg, symptomatic hypotension such as hypotonia, syncope, incontinence, seizure) from pre-infusion measurement, or wheezing, angioedema, or stridor
	
 • Evaluate subject, including close monitoring of vital signs • Treat subject, for example, with: 
 • Normal saline (~500-1000 mL/hour IV) and/or • Diphenhydramine 50 mg IV or equivalent and/or • Acetaminophen 500-650 mg or equivalent dose of paracetamol and/or • IV corticosteroids, such as hydrocortisone 100 mg or methylprednisolone 20-40 mg 	
 • Stop the infusion immediately • Once all symptoms have disappeared, resume current IP infusion under observation and at no more than half the planned infusion rate after treatment of current signs and symptoms as suggested • If severe event recurs in the same subject, discontinue further IP administration

Life threatening
 
Defined as a reaction that is life threatening and requires pressor and/or ventilator support or shock associated with acidemia and impairing vital organ function due to tissue hypoperfusion
	
 • Evaluate subject, including close monitoring of vital signs • Maintain airway, oxygen if available • Treat subject immediately, for example with: 
 • Normal saline (~500-1000 mL/hour IV) • Epinephrine for bronchospasm, hypotension unresponsive to IV fluids, or angioedema. Dose and route as per local standard of care, example, epinephrine 1:1000, 0.5-1.0 mL administered SC for mild cases and intramuscular for more severe cases • IV corticosteroids, such as hydrocortisone 100 mg or methylprednisolone 20-40 mg • Diphenhydramine 50 mg IV or equivalent • Acetaminophen 500-650 mg or equivalent dose of paracetamol • Call emergency medical transport for transport to emergency hospital based on judgment of the investigator 	
 • Stop IP infusion immediately • Do not resume current infusion • Permanently discontinue IP administration • Consider need for additional oral antihistamine administration or oral corticosteroid administration to prevent reoccurrence of symptoms over subsequent 2-3 days

BP = blood pressure; IP = investigational product; IV = intravenous; mmHg = millimeters mercury; SC = subcutaneous.

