4.1.6 Discontinuation of Investigational Product

An individual subject will not receive any further investigational product if any of the following occur in the subject in question:

- 1 Withdrawal of consent for further treatment with investigational product or the subject is lost to follow-up
- 2 An AE that, in the opinion of the investigator or the Sponsor, contraindicates further dosing

- 3 Subject is determined to have met one or more of the exclusion criteria or failed to meet all of the inclusion criteria for study participation and there is a potential safety risk associated with continuation identified upon consultation with the medical monitor
- 4 Pregnancy
- 5 Any of the following liver function abnormalities:
 - (a) ALT or AST $> 8 \times$ ULN
 - (b) ALT or AST $> 5 \times$ ULN for more than 2 weeks (in absence of elevated bilirubin and/or other symptoms listed in item 'd')
 - (c) ALT or AST $> 3 \times$ ULN and total bilirubin $> 2 \times$ ULN or international normalized ratio [INR] > 1.5 ; see Section 5.6.2 for additional details regarding reporting of subjects with ALT or AST $> 3 \times$ ULN and total bilirubin $> 2 \times$ ULN with unknown etiology (ie, Hy's law cases)
 - (d) ALT or AST $> 3 \times$ ULN with the appearance of fatigue, nausea, vomiting, right upper quadrant pain or tenderness, fever, rash, and/or eosinophilia ($> 5\%$)
- 6 Any life-threatening (Grade 4) clinical event including anaphylaxis related to the investigational product as agreed upon consultation with the medical monitor
- 7 Recurrent severe (Grade 3) hypersensitivity reaction related to the investigational product as agreed upon consultation with the medical monitor
- 8 Recurrent severe (Grade 3) infusion reaction related to investigational product as agreed upon consultation with the medical monitor
- 9 Grade 3 or higher neutropenia that does not improve to at least Grade 2 within 5 days as agreed upon consultation with the medical monitor
- 10 Receipt of a prohibited medication in the RCP prior to Day 15 or during the OLP following consultation with the medical monitor (see Section 4.7.2).
- 11 Noncompliance to the study protocol as judged by the investigator and/or the Sponsor

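### Table 3 has sites restart the infusion after reactions that can be anaphylaxis; the Section 4.1.6 stop rules contradict this or leave a first anaphylaxis below Grade 4 to judgement

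*Protocol*

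**What the plan says.** Protocol Section 3.1.3 states that "an approach to these reactions based on severity of symptoms is presented in Table 3 and Appendix 2". Table 3's title names anaphylactic reactions, but the table has no anaphylaxis row. Its five rows are Mild, Moderate (infusion), Moderate hypersensitivity, Severe and Life threatening, each with a product instruction.

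- **Moderate hypersensitivity:** "Infusion reactions which may include generalized rash or urticaria, palpitations, chest discomfort, shortness of breath", or a systolic change above 20 mmHg. Stop, then resume at no more than half rate once the event resolves.
- **Severe:** the signs above plus others, including wheezing, angioedema, stridor, hypotonia, syncope, incontinence or a systolic change of at least 40 mmHg. Stop, then "Once all symptoms have disappeared, resume current IP infusion under observation and at no more than half the planned infusion rate". Product is discontinued only if the severe event recurs.
- **Life threatening:** "Defined as a reaction that is life threatening and requires pressor and/or ventilator support or shock associated with acidemia". Stop, do not resume, discontinue permanently. The treatment cell includes "Epinephrine for bronchospasm, hypotension unresponsive to IV fluids, or angioedema".

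Section 4.1.6 is mandatory: "An individual subject will not receive any further investigational product if any of the following occur in the subject in question". Item 2 is "An AE that, in the opinion of the investigator or the Sponsor, contraindicates further dosing". Item 6 is "Any life-threatening (Grade 4) clinical event including anaphylaxis related to the investigational product as agreed upon consultation with the medical monitor". Items 7 and 8 cover Grade 3 hypersensitivity and infusion reactions, but only recurrent ones, and also after consulting the medical monitor.

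Appendix 2 gives the anaphylaxis criteria. Section 5.4 points the investigator to them for diagnosis but attaches no product action. Appendix 3 defines Grade 4 mainly by an imminent risk of death.

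**The concern.** Table 3 is what a site uses while the infusion is running. If a subject develops generalized urticaria with stridor and the investigator diagnoses anaphylaxis, the matching row still says to restart the same bag once symptoms clear. The rule that names anaphylaxis sits elsewhere and can be read in two ways, and no text says which source governs.

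What is at stake is re-exposing a subject to the product after anaphylaxis. Exclusion criterion 5 keeps out anyone with a history of anaphylaxis after any biologic, with no grade limit, so the protocol already treats this as an unacceptable risk at entry. Section 5.4 says anaphylaxis is rare and usually follows a later exposure. The point therefore bears mainly on the Day 15 dose and the repeated open-label doses every 26 weeks.

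**Working it through.** No design figure is involved. The check compares the sign lists and then the stop rules.

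**Step 1: do the resume rows contain anaphylaxis?** Appendix 2 category 1 needs acute skin or mucosal involvement plus at least one respiratory sign (a) or a blood-pressure or end-organ sign (b). It does not require pressors, ventilation or shock. The skin limb is met by generalized urticaria in the Moderate hypersensitivity row, and the Severe row carries this forward because it adds to the signs above it. The second limb:

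| Example sign in category 1(a)-(b) | Where Table 3 lists it | Product action in that row |
|---|---|---|
| Dyspnea | Moderate hypersensitivity (shortness of breath) | Resume |
| Wheeze-bronchospasm | Severe (wheezing); bronchospasm also in the Life-threatening treatment cell | Resume (Severe row) |
| Stridor | Severe | Resume |
| Reduced peak expiratory flow | Not listed | n/a |
| Hypoxemia | Not listed | n/a |
| Hypotonia | Severe | Resume |
| Syncope | Severe | Resume |
| Incontinence | Severe | Resume |

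That is 1 + 5 = 6 of 8 example signs in rows that say resume. The Life-threatening definition names none of the eight, and its treatment cell names one. Urticaria with shortness of breath (Moderate hypersensitivity), or with stridor or syncope (Severe), can therefore satisfy category 1.

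**Step 2: the blood-pressure route.** Category 3(b) for adults is a systolic pressure below 90 mmHg or a fall of more than 30%. With baseline B:
- A 40 mmHg fall (Severe): B - 40 < 90 when B < 130, and 40/B > 0.30 when B < 133.3.
- A fall just over 20 mmHg (Moderate hypersensitivity): the result is below 90 when B is about 110 or less.

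Category 3 also needs a known allergen, so category 1 is the firmer route.

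**Step 3: what does Section 4.1.6 add?** Of its 11 items, four can be triggered by an infusion or hypersensitivity reaction itself:

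| Item | Trigger | Stops a first anaphylaxis below Grade 4? |
|---|---|---|
| 2 | Investigator or Sponsor opinion | Only if someone judges dosing contraindicated |
| 6 | Grade 4 event including anaphylaxis, with the medical monitor | Depends on the reading |
| 7 | Recurrent Grade 3 hypersensitivity | No, needs recurrence |
| 8 | Recurrent Grade 3 infusion reaction | No, needs recurrence |

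**Step 4: the two readings of item 6.**
- *Anaphylaxis of any grade.* Item 6 says stop while the Moderate hypersensitivity and Severe rows say resume. This is a direct conflict.
- *Grade 4 only (the more literal reading).* Only item 2, 1 of the 4, can stop product for a first anaphylaxis below Grade 4. The Moderate hypersensitivity row has no recurrence clause, so even a repeat graded below 3 rests on item 2. A conflict also remains at Grade 4. Appendix 3 turns on imminent risk of death, whereas Table 3's permanent stop turns on pressor or ventilator support, or shock with acidemia. Stridor judged an imminent risk of death but relieved without that support is a stop under item 6 and a resume under the Severe row.

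Each reading leaves a defect.

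**The case against.** The best counter-argument is that the rules were deliberately aligned and the rest is clinical judgement. On the Grade-4-only reading, items 7 and 8 mirror the Severe row's recurrence clause. Section 4.1.6 is mandatory while Table 3 is presented as an approach, with final treatment left to the investigator, so the stop list should prevail. Item 2 lets the investigator or Sponsor stop alone, and a physician who has diagnosed drug-related anaphylaxis is unlikely to find no contraindication. Section 4.5.3 adds that a dose should be omitted if the subject is not well enough, and that a dose delayed for safety reasons must be discussed with the medical monitor. Epinephrine appears only in the Life-threatening row, so needing it points to permanent discontinuation. Finally, Section 5.4 warns that infusion reactions and anaphylaxis are hard to tell apart, so a strict rule could cost some subjects their treatment.

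Much of this lowers the likely harm, as do the physician on hand, trained staff and emergency equipment. It does not supply the missing rule. The discretion sentence concerns treatment, while the product column is written as instructions; if discretion covers that column too, the reliance on judgement is confirmed. No text ranks Section 4.1.6 above Table 3. Section 4.5.3 is another judgement rule and does not mention anaphylaxis. Nothing says that giving epinephrine moves a reaction into the Life-threatening row, and angioedema is itself a listed Severe sign. The sign count also has limits: it counts single signs although category 1 needs a combination, and it treats shortness of breath as dyspnea. It shows overlap, not frequency. The risk of misclassification stands as a cost of the fix.

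**Conclusion.** The concern holds and should be fixed. Two of the four resume rows in Table 3 can contain an Appendix 2 anaphylaxis, and only the Life-threatening row stops product permanently at a first event. Depending on how item 6 is read, Section 4.1.6 either contradicts those rows, or leaves a first anaphylaxis below Grade 4 to opinion and still disagrees with Table 3 on some Grade 4 reactions.

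The conclusion rests on the signs occurring together, on the investigator making the diagnosis under Section 5.4, and on the text available. Part of the infusion-reaction risk text in Section 1.4 and the Investigator's Brochure were not available for this check. The documents give no rate of such reactions, so the number of subjects affected is not estimated. This is a subject-safety inconsistency with no bearing on power, Type I error or the efficacy analyses.

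**What to change.** 1. Add to Table 3 that any reaction the investigator diagnoses as anaphylaxis, using Appendix 2 and the Section 5.4 advice, and any Grade 4 reaction under Appendix 3, follows the Life-threatening row's product instruction: stop, do not resume, discontinue permanently.
2. Reword Section 4.1.6 item 6 so that it covers two things separately: a Grade 4 event, or anaphylaxis of any grade, in each case related to the product. Make the stop immediate, with the medical monitor consulted afterwards.
3. Leave items 7 and 8 and the Severe row's recurrence clause unchanged for reactions that are not anaphylaxis.

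The cost is wording in one table and one list item, plus a notice to sites. No new procedure is needed. The downside is that some subjects with a borderline diagnosis would lose the Day 15 or open-label doses, in a disease that the protocol says has no approved treatment. Without a reaction rate, that loss cannot be sized.

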3.2 Study Design and Dose Rationale

3.2.1 Study Design Rationale

This study design was developed to provide balance between scientific considerations and patient safety. A placebo-comparator treatment arm was chosen because there are no currently approved medications for the treatment of NMO/NMOSD. While there is anecdotal evidence for using various immunosuppressants in NMO/NMOSD, the efficacy and safety profiles of these agents are not well characterized because there have been no controlled clinical studies using these agents in this disease indication. The use of a placebo arm will allow for a clear and robust evaluation of MEDI-551 and provide for the highest sensitivity to detect efficacy. The therapeutic estimation of the potential effect of MEDI-551 is based on published literature, albeit uncontrolled data, showing that B-cell depletion may have a positive effect in preventing NMO/NMOSD attacks. The Sponsor expects that MEDI-551 will share the same class effects that have been seen with other B-cell depleting agents in subjects with NMO/NMOSD.

A 3:1 randomization scheme was chosen for this study. According to [Dumville et al \(2006\)](#), unequal randomization is particularly useful when the experimental group is expected to benefit greatly from a new treatment that would not have been otherwise available and can provide the clinician with a reduced learning curve by allowing treatment in a higher percentage of subjects ([Dumville et al, 2006](#)). The 3:1 randomization ratio is an effective and efficient approach to build an enriched safety database for MEDI-551 while keeping the number of required events or subjects in the placebo arm at a minimum acceptable level. This randomization ratio also addresses, to a certain degree, the serious ethical/safety concerns of investigators and patients regarding enrollment of subjects to a placebo arm. In addition to limiting the number of subjects who receive placebo, the study has been designed to limit the actual duration of placebo exposure to a maximum of 197 days or time to onset of an AC-determined NMO/NMOSD attack, whichever occurs earlier, after which all subjects will have the option to enter the OLP and receive MEDI-551.

Due to the potential severity of NMO/NMOSD attacks and their debilitating nature, the study is further designed to ensure safety in this subject population through careful monitoring and early evaluation of signs and symptoms of NMO/NMOSD attacks, scheduled study visits and study assessments, follow-up telephone contact every 2 weeks with study subjects by study site staff, a liberal “escape clause” (ie, immediate access to rescue therapy following identification of an NMO/NMOSD attack), and monitoring by an independent Data Monitoring Committee (DMC).

Also, the informed consent form (ICF), which will include detailed explanation and risk:benefit expectations, will provide subjects and investigators the opportunity to discuss

appropriate risk estimation and to fully understand the risks and potential benefits of this study.

The rationale for the use of oral corticosteroids (prednisone 20 mg/day or equivalent oral glucocorticoid) for the first 14 days, with a 1-week taper, is to provide prophylaxis against an NMO/NMOSD attack for the period wherein the PD effect of MEDI-551 is not expected. Based on our PK/PD data, a period of approximately 2-4 weeks is required for maximal B-cell depletion to occur.

In addition, studies with rituximab have reported a few attacks in the first month of therapy possibly related to increased B-cell activating factor (BAFF; [Bar-Or et al, 2010](#)) and therefore an increase of AQP4-IgG titers. Feedback from external experts has suggested that providing such prophylaxis is viewed as particularly important in a setting where existing immunosuppressive regimens will be withdrawn at randomization.

[figure not shown]
